6. PRIMARY OUTCOME MEASURE

The primary outcome will be unassisted patency six weeks after fistula creation. Fistula patency will be determined by physical examination of the fistula performed by trained study personnel. The fistula will be classified as patent if a bruit is present throughout systole and diastole. The bruit must be detectable along the vein at least 8 centimeters proximal to the arteriovenous anastomosis. In a quality control subset of patients the outcome will be independently assessed by at least one trained member of the study team and a second person.

The fistula patency outcome will be ascertained at 6 weeks in all patients except those in whom study drug was discontinued because of fistula thrombosis prior to six weeks. To allow patients with fistula thrombosis and no restoration of patency to complete study participation within 30 days of study drug discontinuation, the fistula patency outcome assessment may be completed at any time within the 30 days following study drug discontinuation.

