2.2 Design

The trial is a randomized, double-blind, placebo-controlled multi-center trial with a parallel treatment design. Patients with chronic renal failure who are on chronic hemodialysis or anticipated to begin chronic hemodialysis within 6 months will be randomized within one calendar day following creation of a new upper extremity native AV fistula to receive either clopidogrel or placebo for six weeks. Randomization will be on a 1:1 active drug:placebo allocation, and will be stratified by Clinical Center and location of AV fistula (forearm vs upper arm). Both patients and study personnel will be masked to treatment assignment. The sample size is 1284 patients, to be recruited at seven Clinical Centers over a 4-year period. Study drug administration will begin within one calendar day following native AV fistula creation and continue for 6 weeks following surgery. The primary outcome measure is fistula patency at the end of the 6-week study drug administration period. A secondary outcome measure is fistula suitability for dialysis.

A follow-up evaluation will be conducted six weeks following creation of the AV fistula. Fistula patency (primary outcome) will be ascertained at that visit. Contact will be made with the patient and/or dialysis unit on a monthly basis thereafter to obtain data related to the fistula suitability for dialysis outcome. All randomized patients who undergo creation of a native fistula will be followed regardless of whether or not they remain on their assigned treatments. Participation in the study will end once the fistula suitability outcome has been ascertained. Fistula suitability outcome ascertainment will occur during the fourth month following fistula creation for those patients who are either on chronic hemodialysis at the time of fistula creation or begin hemodialysis within 4 months of fistula creation. If dialysis is not initiated within 4 months of fistula creation, ascertainment of fistula suitability for dialysis will occur during the first month

of hemodialysis. If the fistula has not been used at the time of the suitability assessment, but may be used in the future, the patients will continue to be followed until it is determined whether the fistula is actually used.

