4.4.6 Fistula Thrombosis Within the First Six Weeks Following Fistula Creation Surgery

If fistula thrombosis occurs prior to randomization, the patient should not be randomized to treatment group and study participation will end. If fistula thrombosis occurs after randomization, study drug will be discontinued. Study drug should not be discontinued for thrombosis unless thrombosis is confirmed by a member of the study team or by the patient's surgeon. The duration of study participation after fistula thrombosis will depend on whether fistula patency is restored. If fistula patency is not restored, study participation will end 30 days after the study drug is discontinued. If fistula patency is restored, the patient will remain off the study drug, but participation in the study will continue until the ascertainment of fistula suitability for dialysis.

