7.2 Fistula suitability for dialysis without radiological or surgical modification

Suitability for dialysis criteria is defined as in Section 7.1 except that the fistula cannot be modified radiologically or surgically. Modified fistulae will be considered to have failed on the date of modification.

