8.2.2.2 Outcome Measures

Primary Analysis of Fistula Patency at 6 Weeks

The primary analysis will evaluate the effect of randomization to clopidogrel vs. placebo on the probability that a new fistula will be patent six weeks after randomization. This analysis will be carried out by applying the Mantel-Haenszel test to compare the proportion of patent fistulas at six weeks with stratification for Clinical Center and the location of the fistula. The comparison of the clopidogrel and placebo interventions in the primary analysis will be carried out using an intent-to-treat strategy in which patients are retained in their randomized groups regardless of their compliance to the treatments. A 2-sided hypothesis test will be conducted at the 5% level of significance.

Analyses of Secondary Outcomes

The Mantel-Haenszel test (with stratification for Clinical Center and fistula location) will also be used to evaluate the effect of randomization to clopidogrel on the two main secondary outcomes:

- a. the proportion of fistulae suitable for dialysis with or without radiological or surgical modification in the two treatment groups (secondary outcome measure).
- b. the proportion of fistulae suitable for dialysis without radiological or surgical modification in the two treatment groups (secondary outcome measure).

Other Secondary Analyses

Secondary analyses will include an analysis of the three outcome measures for patients in whom study drug is not deliberately discontinued during the six week study drug administration period. Study outcomes will also be analyzed using logistic regression and adjusting for additional covariates found by interactive data analysis to be predictive of the primary or secondary outcomes. Death rates in active drug and placebo groups will also be compared.

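### The primary outcome is called unassisted patency, but the only classification rule is a bruit, so fistulae reopened or modified before the six-week assessment have no consistent classification

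*Protocol*

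**What the plan says.** Section 6 opens with the endpoint: "The primary outcome will be unassisted patency six weeks after fistula creation". It then gives the rule for classifying a fistula: "The fistula will be classified as patent if a bruit is present throughout systole and diastole". One further condition follows: "The bruit must be detectable along the vein at least 8 centimeters proximal to the arteriovenous anastomosis". Neither condition mentions what happened to the fistula before the examination.

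The other statements of the outcome are:

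- Section 2.2: "The primary outcome measure is fistula patency at the end of the 6-week study drug administration period".
- Section 4.1: patency at the second visit is judged by the presence of a bruit.
- Section 5.3: the patency item is the bruit criterion with the 8 cm condition.
- Section 8.1: the primary outcome is called fistula thrombosis at 6 weeks, planned at 25% on placebo with a 30% relative reduction.
- Section 8.2.2.2: the test is to "compare the proportion of patent fistulas at six weeks".

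Reopened fistulae are expected. Section 4.4.6 says "If fistula patency is restored, the patient will remain off the study drug, but participation in the study will continue". On timing, Section 6 requires ascertainment at six weeks in all patients "except those in whom study drug was discontinued because of fistula thrombosis prior to six weeks". The reason given for the alternative timing concerns only patients whose patency was not restored.

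Both secondary outcomes deal with modification explicitly. Section 7.1 counts modified fistulae as suitable. Section 7.2 says "Modified fistulae will be considered to have failed on the date of modification".

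**The concern.** The single primary endpoint has a name that excludes assisted fistulae and a working rule that does not. Two groups fall between them: fistulae that thrombosed and were reopened, and fistulae that had angioplasty or another modification without thrombosing. Either kind can have a qualifying bruit at the assessment.

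If such patients were classed by bruit alone, some true early failures would leave the event count and the absolute difference between arms would shrink. The result would also depend partly on local practice. Section 1.1 says many operators will not attempt declotting of native fistulae, and Section 3.3 expects regional differences in practice. If they were classed by the label, the event would be wider than the thrombosis rate on which 8.1 is built. Either choice can be defended, but the protocol should make it rather than leave it to whoever codes the outcome.

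**Working it through.** **1. The statements side by side.** *Unassisted* is taken in its ordinary sense, because the protocol does not define it.

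| State at the assessment | Label in Section 6 | Literal bruit rule | Event in 8.1 (thrombosis) |
|---|---|---|---|
| Qualifying bruit, no thrombosis, no procedure | success | patent | no |
| Qualifying bruit, thrombosed then reopened | failure | patent | thrombosis occurred; whether it counts once reopened is not stated |
| Qualifying bruit, modified without thrombosis | failure | patent | no |
| No qualifying bruit, no thrombosis | failure | not patent | no |

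The second and third rows are the conflict between label and rule. The third and fourth rows show failures that are not thromboses, and so are additional to the 25% in 8.1.

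**2. Reproducing the sample size.** Inputs from Section 8.1: 25% versus 0.70 × 25% = 17.5%; 85% power; two-sided alpha 0.05; 3% drop-in; 3% drop-out; 5% loss; 2.7% inflation for the stopping rule.

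- Diluted placebo rate: 0.97 × 0.25 + 0.03 × 0.175 = 0.24775.
- Diluted clopidogrel rate: 0.97 × 0.175 + 0.03 × 0.25 = 0.17725.
- Formula, with pooled variance under the null and p̄ the mean of the two rates: n = [1.960 √(2p̄(1−p̄)) + 1.036 √(p₁(1−p₁) + p₂(1−p₂))]² / (p₁−p₂)².
- Result: n = 604 per arm. Then 604 × 1.027 / 0.95 = 653 per arm, or 1306 in total.

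The plan's 1284 is reproduced to within 1.7%, so the sample-size arithmetic is not in question.

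**3. Effect of classing rescued thromboses as patent.** Let f be the share of thromboses that are reopened and have a qualifying bruit at the assessment. The documents give no value for f. It is assumed equal in both arms, and both diluted rates are multiplied by (1−f). The 30% relative reduction is unchanged, but the absolute difference shrinks.

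Power uses the same variance terms, with an equivalent fixed-design size of 642 × 0.95 / 1.027 = 594 per arm. The reclassified counts use 642 × 0.95 ≈ 610 evaluable per arm multiplied by the diluted rate and by f.

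| f | Undiluted rates | Power at 1284 | Total N for 85% power | Reclassified, placebo / clopidogrel |
|---|---|---|---|---|
| 0 | 25% vs 17.5% | 84.5% | 1306 | 0 / 0 |
| 2% | 24.5% vs 17.15% | 83.5% | 1340 | 3 / 2 |
| 5% | 23.75% vs 16.6% | 82.1% | 1394 | 8 / 5 |
| 10% | 22.5% vs 15.75% | 79.5% | 1490 | 15 / 11 |

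The table covers rescued thromboses only. Nothing in the documents allows the number of fistulae modified without thrombosis to be estimated.

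**The case against.** The strongest reply is that the first sentence of Section 6 governs. On that view *unassisted* defines the endpoint, the bruit is only how patency is examined, and both conditions apply. Sections 2.2 and 8.2.2.2 would then be using shorthand. Counting thrombosis as failure in 8.1 fits the label, and leaves the planning rates and the 1284 as they are. This is a reasonable reading and may be what was intended. It rests, however, on one undefined word that appears neither in the classification rule nor in the analysis section, and it does not say which interventions count as assistance.

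A reader might infer something stronger: that the protocol turns rescued fistulae into successes. The documents do not support that. No sentence says so. It follows only if the bruit rule is applied literally and the label is set aside. Section 6 also takes patients whose drug was stopped for thrombosis out of the routine six-week ascertainment. That exception does not settle the matter, because it leaves the classification of restored fistulae unstated.

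A reader might also infer a large loss of power. The same calculation gives 73.5% at f = 20%. Section 1.1 speaks against shares of that size: thrombosis usually ends in abandonment, surgically reopened fistulae often clot again early, and many operators will not try. Only rescues still patent at the assessment matter here.

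Finally, treating every modification as failure widens the event beyond thrombosis. That objection stands, and the fix has to acknowledge it in 8.1.

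**Conclusion.** The point holds as an inconsistency in the definition of the primary endpoint. The label and the stated rule classify the same fistula differently, and reopened or modified fistulae have no stated classification. This is more than a detail left for later, because the protocol sets the endpoint itself and its sections disagree on what counts as an event. It is not a stated rule that rescued fistulae succeed, and it is not a sample-size error.

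The numerical effect is illustrative and probably small. It costs about 1 to 5 percentage points of power if 2% to 10% of thromboses were rescued and classed as patent, with the low end more plausible from Section 1.1. These figures assume the same rescue share in both arms and the planning rates of 8.1. If the label is applied, this loss does not arise.

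**What to change.** State in Section 6 that primary success requires a qualifying bruit at the assessment, and no confirmed thrombosis and no radiological or surgical modification of the fistula between randomization and that assessment. Add that fistulae with restored patency count as failures. This parallels the rule already written in 7.2 and closes the gap left by the timing exception.

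Use the same outcome name in 2.2, 4.1, 5.3, 8.1 and 8.2.2.2. In 8.1, note that the 25% planning rate is a thrombosis rate, so failures from non-thrombotic modification or from an absent qualifying bruit are additional to it. Report bruit at six weeks regardless of assistance as a sensitivity analysis.

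The cost is small: wording changes and one further analysis. Section 5.3 already records procedures on the fistula and their dates at the six-week visit.

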7. SECONDARY OUTCOME MEASURES

7.1 Fistula Suitability for Dialysis

Suitability for dialysis is defined as the ability to use the fistula for dialysis for at least 4 weeks and obtain a minimal nominal dialysis blood flow of 300 ml/min. To meet the 300 ml/min dialysis blood flow criterion all blood flow measurements recorded after the first hour and before the last 15 minutes of the dialysis session must be ≥ 300 ml/min. In order to distinguish fistula inadequacy from poor dialysis needle placement which might occasionally occur and result in low blood flow, the requirement for nominal blood flow of ≥ 300 ml/min must be met during at least 8 dialysis treatments during the 12-session ascertainment period. Fistulae suitable for dialysis will include those modified radiologically or surgically. Radiological modification may include percutaneous balloon angioplasty of stenoses, or pharmacological or mechanical thrombolysis. Surgical modification may include thrombectomy, or revision of the arteriovenous anastomosis as long as the same artery and vein are used.

The fistula suitability outcome ascertainment will begin 120 days after creation of the fistula for patients on dialysis prior to creation of the fistula. For patients who have not initiated dialysis at the time of fistula creation, fistula suitability ascertainment will begin 120 days after fistula

creation if dialysis is initiated within 4 months of fistula creation, or at the onset of initiation of dialysis if dialysis is initiated more than 4 months after fistula creation. The fistula will be considered suitable if the machine blood flow requirements are met for 8 of 12 consecutive dialysis sessions that take place. The first of these 12 sessions must occur between 120 and 150 days after fistula creation. For patients who initiate dialysis >120 days after fistula creation the suitability ascertainment period will begin with the first dialysis session and will end with the 12th consecutive dialysis session that takes place, or by 60 days after initiation of dialysis, whichever comes earlier.

Initial unsuccessful use of the fistula will not preclude attainment of the fistula suitability outcome as long as suitability criteria are met during the ascertainment periods described above.

7.2 Fistula suitability for dialysis without radiological or surgical modification

Suitability for dialysis criteria is defined as in Section 7.1 except that the fistula cannot be modified radiologically or surgically. Modified fistulae will be considered to have failed on the date of modification.

8. STATISTICAL DESIGN

8.1 Sample Size Calculations

From review of the literature, it is estimated that fistula thrombosis at 6 weeks (primary outcome) will occur in 25% of patients treated with placebo and failure to achieve fistula suitability for dialysis (secondary outcome) will occur in 40% of patients treated with placebo^{14, 28-35, 48}. In order to detect a 30% reduction in fistula thrombosis rate with 85% power and a 2 sided-alpha level of 0.05, 1284 patients are required (642 in each treatment group) assuming a 5% loss to follow-up rate, a 3% treatment drop-in rate, and a 3% treatment drop-out rate. This sample size also includes a slight (2.7%) upward adjustment to account for the O'Brien-Fleming stopping rule suggested by the Steering Committee. Under a fixed sample size design, the sample size of 1,284 would provide approximately 80% power to detect a 20% reduction in failure to achieve fistula suitability for dialysis.

Addendum: As of June 1, 2004 the recruitment period of the study was extended from 48 to 51 months based on the recommendation of the Data Safety and Monitoring Board (External Advisory Committee).

8.2 Data Analysis

8.2.1 Interim Monitoring and Analysis

The External Advisory Committee will monitor the safety of the patients during the course of the study and evaluate interim analyses of efficacy performed by the Data Coordinating Center. The Steering Committee recommends that the External Advisory Committee consider a formal statistical stopping guideline based on a spending function with an O'Brien-Fleming boundary based on 5 annual looks at the data, including 4 interim and 1 final analysis.

8.2.2 Final Analysis

8.2.2.1 Baseline Comparability

To assess external generalizability, demographic, clinical, and dialysis treatment characteristics of patients who are randomized will be summarized to characterize the study

population and then contrasted with the characteristics of patients who are screened but not randomized. The randomized patients will also be compared to the general population of hemodialysis patients characterized in the USRDS. The specific eligibility and exclusionary criteria by which patients are excluded from randomization will be tabulated. Demographic and clinical characteristics will be compared among the Clinical Centers and between the randomized treatment groups to identify any imbalances.

8.2.2.2 Outcome Measures

Primary Analysis of Fistula Patency at 6 Weeks

The primary analysis will evaluate the effect of randomization to clopidogrel vs. placebo on the probability that a new fistula will be patent six weeks after randomization. This analysis will be carried out by applying the Mantel-Haenszel test to compare the proportion of patent fistulas at six weeks with stratification for Clinical Center and the location of the fistula. The comparison of the clopidogrel and placebo interventions in the primary analysis will be carried out using an intent-to-treat strategy in which patients are retained in their randomized groups regardless of their compliance to the treatments. A 2-sided hypothesis test will be conducted at the 5% level of significance.

Analyses of Secondary Outcomes

The Mantel-Haenszel test (with stratification for Clinical Center and fistula location) will also be used to evaluate the effect of randomization to clopidogrel on the two main secondary outcomes:

- a. the proportion of fistulae suitable for dialysis with or without radiological or surgical modification in the two treatment groups (secondary outcome measure).
- b. the proportion of fistulae suitable for dialysis without radiological or surgical modification in the two treatment groups (secondary outcome measure).

Other Secondary Analyses

Secondary analyses will include an analysis of the three outcome measures for patients in whom study drug is not deliberately discontinued during the six week study drug administration period. Study outcomes will also be analyzed using logistic regression and adjusting for additional covariates found by interactive data analysis to be predictive of the primary or secondary outcomes. Death rates in active drug and placebo groups will also be compared.

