4.4.4 Discontinuation of Therapy

Events leading to cessation of study drug, but not termination from the study will include:

1. Removal from hemodialysis because of transplantation, recovery of renal function, or use of other dialysis modality.
2. A medical event which contraindicates continued use of an antiplatelet agent during the six week study drug period.
3. Any bleeding episode which contraindicates the continued use of antiplatelet agents during the six week study drug period. Such events include, but are not limited to, major bleeding defined as confirmed retroperitoneal, intra-articular, or cerebral hemorrhage or any bleeding

episode resulting in a 2 g/dl decrease in the hemoglobin concentration and requiring hospitalization or transfusion.

4. An adverse event attributed to the study medication without other etiology that does not respond to medical management.
5. An acute cardiovascular event requiring antiplatelet therapy.
6. Native fistula thrombosis during the six-week study drug administration period. Thrombosis must be confirmed by a member of the study team or by the patient's vascular surgeon. Participation in the study will end 30 days after discontinuation of the study drug if fistula patency is not restored by thrombectomy or thrombolysis. If fistula patency is restored, the patient will remain off study drug, but will remain in the study until the fistula suitability for dialysis is ascertained.

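### The secondary analysis limited to patients whose study drug was not deliberately stopped drops patients because they had the primary failure event, since confirmed thrombosis obliges the drug to be stopped

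*Protocol*

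**What the plan says.** Under Other Secondary Analyses, Protocol Section 8.2.2.2 provides for an analysis of the three outcome measures "for patients in whom study drug is not deliberately discontinued during the six week study drug administration period". The three are unassisted patency at six weeks (Section 6), suitability for dialysis (Section 7.1) and suitability without modification (Section 7.2).

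Section 4.4.4 opens its list with "Events leading to cessation of study drug, but not termination from the study will include", and item 6 of the list is "Native fistula thrombosis during the six-week study drug administration period". Section 4.4.6 makes the stop obligatory: "If fistula thrombosis occurs after randomization, study drug will be discontinued". It adds a condition, "Study drug should not be discontinued for thrombosis unless thrombosis is confirmed by a member of the study team or by the patient's surgeon", and keeps the drug off after a successful rescue: "If fistula patency is restored, the patient will remain off the study drug".

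Section 6 defines the endpoint: "The primary outcome will be unassisted patency six weeks after fistula creation". When it sets the timing of assessment it refers to "those in whom study drug was discontinued because of fistula thrombosis prior to six weeks", so the protocol itself treats thrombosis as a cause of stopping. Section 8.1 equates failure of the primary outcome with fistula thrombosis at six weeks. The protocol neither defines *deliberately* nor exempts stops caused by thrombosis.

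**The concern.** A stop that the protocol requires, made only after a study team member or the surgeon has confirmed the thrombosis, is deliberate in the ordinary sense of the word. Membership of the analysis set therefore depends on the outcome being analysed: a patient leaves the set because the fistula failed. If clopidogrel works, more patients leave from the placebo arm.

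This is the only analysis the protocol names that is restricted by drug exposure, and a reader would look to it for the effect in patients who stayed on treatment. Built as worded, it cannot answer that question, because it discards patients who were still on drug when their fistula thrombosed. Two analysts who read *deliberately* differently would also build different sets.

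**Working it through.** **Inputs.** From Section 8.1: placebo thrombosis 25%; a 30% reduction, so 17.5% on clopidogrel; placebo suitability failure 40%; a 20% reduction, so 32%; 642 per arm; 5% loss, so 642 × 0.95 ≈ 610 followed per arm; two-sided 5% test. One input is not in the protocol: q, the share of thromboses confirmed and followed by a drug stop before the six-week visit. It is an assumption, shown over a range.

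**Reproducing the plan's figure.** With 3% drop-in and 3% drop-out the rates become 24.775% (0.97 × 25% + 0.03 × 17.5%) and 17.725% (0.97 × 17.5% + 0.03 × 25%). At 85% power, without continuity correction, 604 per arm are needed. Then 2 × 604 / 0.95 × 1.027 ≈ 1306, within 2% of the stated 1284. This confirms only that the design rates are read correctly.

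**Patency in the retained set.** For an arm with thrombosis rate p:
- retained patients = 610(1 − pq)
- failures left = 610p(1 − q)
- failure rate = p(1 − q)/(1 − pq)

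Example at q = 0.8:
- placebo: 0.25 × 0.2 / (1 − 0.20) = 0.0625
- clopidogrel: 0.175 × 0.2 / (1 − 0.14) = 0.0407

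Power is from a normal approximation with no further dilution.

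| q | Retained, placebo / clopidogrel | Failures left | Failure rate | Difference | Power |
|---|---|---|---|---|---|
| 0 | 610 / 610 | 153 / 107 | 25.0% vs 17.5% | 7.5 points | 0.89 |
| 0.5 | 534 / 557 | 76 / 53 | 14.3% vs 9.6% | 4.7 | 0.67 |
| 0.8 | 488 / 525 | 31 / 21 | 6.3% vs 4.1% | 2.2 | 0.35 |
| 0.9 | 473 / 514 | 15 / 11 | 3.2% vs 2.1% | 1.1 | 0.20 |
| 1 | 458 / 503 | 0 / 0 | 0% vs 0% | none | none |

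**Odds ratio.** The failure odds in the retained set are p(1 − q)/(1 − p). The odds ratio is therefore [(0.175/0.825) / (0.25/0.75)] × (1 − q on clopidogrel)/(1 − q on placebo) = 0.64 × (1 − q on clopidogrel)/(1 − q on placebo).
- Equal q: it stays at 0.64 for any q below 1. The risk ratio moves from 0.70 to 0.65 at q = 0.8.
- q = 0.9 on placebo and 0.5 on clopidogrel: 3.2% vs 9.6%, a reversal.
- q = 0.5 on placebo and 0.9 on clopidogrel: 14.3% vs 2.1%, an exaggerated benefit.

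**Suitability.** If every thrombosed fistula is unsuitable, the failure rate F becomes (F − pq)/(1 − pq). At q = 0.8:
- placebo: (0.40 − 0.20)/0.80 = 25.0%
- clopidogrel: (0.32 − 0.14)/0.86 = 20.9%

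The difference falls from 8.0 to 4.1 points. The odds ratio moves from (0.32/0.68)/(0.40/0.60) = 0.71 to (0.209/0.791)/(0.25/0.75) = 0.79, towards no effect.

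**The case against.** A reader might infer that the analysis would show no drug effect on patency. The protocol does not support that. With equal q the patency odds ratio is preserved, and the planned Mantel-Haenszel test and logistic regression both work naturally on the odds scale. Bias on that scale needs q to differ by arm, and double-blinding (Section 3.4) gives some protection against that. This stands, and it limits the patency damage under equal detection to lost events, absolute difference and power.

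A reader might also infer that practically every failure is removed. That too goes further than the text. After the contact on the first working day following surgery, the next scheduled contact is the six-week visit (Section 4.1), and monthly contacts begin only after it (Section 5.4). Many eligible patients are not yet on dialysis (Section 11). Thromboses first found at the visit stay in the set, as do fistulae that fail the bruit criterion without confirmed thrombosis. A high q therefore has no source, and even at 0.8 about 31 vs 21 failures remain.

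The suitability figures assume that no thrombosed fistula becomes usable, whereas Section 7.1 counts fistulae rescued by thrombectomy or thrombolysis. Section 1.1 says abandonment is usual, so the assumption is a fair approximation but not exact.

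Finally, the authors may have meant only stops for other reasons, and on-treatment sets are often defined in an analysis plan. The intent is possible, but here the protocol does state the set in words, and those words take in stops for thrombosis.

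**Conclusion.** The point holds at moderate severity. As worded, the restriction in Section 8.2.2.2 selects on the primary failure event. At the design rates the patency difference falls from 7.5 points to 4.7 at q = 0.5 and to 2.2 at q = 0.8, and power falls from about 0.89 to 0.67 and 0.35. At q = 1 no confirmed thrombosis is left to compare. The patency odds ratio survives only if q is equal in the two arms; otherwise the estimate is biased and may change direction. The suitability contrast is attenuated even with equal q, given the assumption that thrombosed fistulae are unsuitable. All these sizes depend on q, which the protocol does not give.

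It would be wrong to conclude that the trial's main result is at risk. The intent-to-treat primary test, the two main secondary comparisons by randomized group and the sample size do not use this set.

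**What to change.** In Section 8.2.2.2, add that a study drug stop caused by fistula thrombosis does not exclude the patient. That patient stays in the set with the observed outcome: failure for unassisted patency, and suitability as ascertained. Only stops for other reasons, made before any thrombosis, exclude. With no other exclusions this restores the design contrast of 25% vs 17.5%.

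The change does not remove all selection. Stops for bleeding and other reasons would still exclude, and Section 5.5 names bleeding as the major expected risk of clopidogrel, so these exclusions may be related to arm. The analysis must be read as supportive only.

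The cost is about one sentence, best settled before unblinding. Section 5.3 (item 7) already collects the reason for study drug interruption, so no new data are needed. The clinical stopping rule does not change.
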